Given the risk of clinical reactions to peanut allergen with accidental unintentional exposures and the impact of peanut avoidance on the quality of life of peanut allergic subjects (21), peanut immunotherapy as an effective treatment is an unmet need. This effective therapeutic procedure with an acceptable safety profile is needed in more academic centers around the country. Subjects receiving this therapy need close monitoring through expert centers to treat potential systemic symptoms. The immune determinants of clinical tolerance are still not completely understood. The goal of this proposed trial is to utilize the efficacy of oral immunotherapy to study the safety of peanut oral immunotherapy and evaluate immune mechanisms of clinical tolerance, using technology to identify T cell cytokine responses and subsets by flow cytometry. This trial will also expand the availability of this therapy to subjects in the southern United States.

All subjects will receive the peanut protein intervention. There is no placebo control for this study. In order to meet inclusion criteria subjects will not be able to tolerate a 1 gram peanut protein challenge. The primary outcome to be studied is the safety of the therapy and the secondary outcome will include changes in T and NKT cell function and intracellular cytokine expression from peanut allergic subjects during peanut OIT. We will look at both the initial response to building up the dose and changes during the maintenance phase. We are requesting a target enrollment of 15 subjects. Subjects will be recruited from the Texas Children's Hospital Allergy and Immunology Clinic. Subjects are expected to participate for a total of 38 months. After screening visits, the study will require approximately 33 visits with 2 phases: the build-up phase (weeks 0-50), followed by the maintenance phase (2 years).

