2. OBJECTIVES

2.1 *Primary Objectives:*

- 2.1.1. The primary objective is to determine whether peanut oral immunotherapy safely develops clinical tolerance in peanut allergic patients by assessing the change of dose tolerated and to determine the percentage of subjects who can tolerate 6 g of peanut flour with absence of clinical symptoms during a food challenge following the initial desensitization phase of peanut flour which includes a 50 week dose escalation phase and 104 week maintenance phase on a peanut equivalent dose.

2.1. Secondary Objectives:

To determine the immune mechanisms of clinical tolerance, using technology to identify T cell cytokine responses and subsets, as well as basophil activation responses as measured by flow cytometry. T and NKT cell function and intracellular cytokine expression will be measured.

2.2.1. To determine whether viral exposure potentiates response to in vitro peanut allergen exposure and to assess those changes during peanut OIT.

2.2.2. To compare the change in dose tolerated after one month of abstaining from peanut to determine sustained unresponsiveness.

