3. PATIENT ENROLLMENT CRITERIA

3.1. Inclusion Criteria:

Subjects who meet all of the following criteria are eligible for enrollment as study participants:

- Age 5-16 years of either sex, any race, any ethnicity, weighing at least 18.3 kg at the time of the initial visit.
- The presence of IgE specific to peanuts (a positive skin prick test to peanuts (diameter of wheal >3.0 mm) and a positive in vitro IgE [CAP-FEIA] > 7 kU/L).
- Significant clinical symptoms occurring within 120 minutes after ingestion of the last tolerated dose of peanut protein during the DBPCFC. Patients who have not had previous oral exposure to peanut will be observed for a longer duration of 150 minutes because they may demonstrate a delayed immune response, given the lack of prior peanut exposure. Also, patients with a history of prior anaphylaxis will be observed for 150 minutes. (21-24)
- Provide signed informed consent.
- Ability to follow-up regularly for scheduled appointments.
- Subjects will not be excluded if they are primarily Spanish speaking.
- Females of childbearing potential must be willing to practice an acceptable form of birth control throughout the protocol.
- Epinephrine injection training provided
- Participant has current in-date epinephrine injector and parent/guardian demonstrates proper use.

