- DBPCFC: Subjects eligible for the study (peanut-specific immunoglobulin E level greater than 7kU/L AND a positive skin prick test to peanut) will come to Texas Children's Hospital in Houston for a Double Blind Placebo Controlled Food Challenge (DBPCFC) to the study protein to determine if the subject is allergic to peanut. The table below labeled Table 2 details dosing for the initial DBPCFC and also shows the dose at which the subject will start treatment correlating with the dose at which a reaction is noticed.

Table 2. Entry Double-Blinded Placebo Controlled Food Challenge Protocol and Starting Dose of Oral Immunotherapy to be Initiated				
Dose Number	Approximate Dose Weight (PEANUT FLOUR)	Approximate Dose Weight (PEANUT PROTEIN)	Cumulative Dose Weight (peanut protein)	Starting Dose of OIT if Subject Reacts
1	1 mg	0.5 mg	0.5 mg	Ineligible
2	2 mg	1 mg	1.5 mg	Ineligible
3	10 mg	5 mg	6.5 mg	1.8mg
4	30 mg	15 mg	21.5 mg	3.6 mg
5	108 mg	54 mg	75.5 mg	14.4 mg
6	150 mg	75 mg	150.5 mg	28.8 mg
7	200 mg	100 mg	250.5 mg	40 mg
8	500 mg	250 mg	500.5 mg	120 mg
9	1000 mg	500 mg	1000.5 mg	300 mg
10	2000 mg	1000 mg	2000.5 mg	750 mg

The DBPCFC visit will last approximately 9 hours. The food challenge may be performed in one day or split into two days. The subject will discontinue antihistamines (for example Zyrtec or Claritin) for 7 days before the procedure and must be off oral corticosteroids for one month before the food challenge.

A DBPCFC consists of eating both a food to which the subject may be allergic (peanut) and eating a placebo at different times. A placebo is a substance that is similar to the test substance in appearance, smell, and taste. The peanut protein is a flour and will be given mixed with either juice (at lower doses) or with a food like baby food. The placebo is oat flour for peanut DBPCFC and will be given in the same manner.

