Peanut equivalent will be used for the food challenge at 0 month maintenance food challenge. The challenge will consist of increasing doses of peanut (in the form of peanut equivalent) given every 15 minutes in increasing amounts (Table 5). The other challenge will consist of placebo material given also in increasing doses. The highest dose will be equivalent to approximately 34 peanuts.

- Review Home Symptom Diary: We will review any symptoms experienced while taking the food protein.
- Urine Pregnancy Test: For females of reproductive potential a urine pregnancy test will be performed prior to the food challenge. If the subject is pregnant the food challenge will not be performed and the subject will be dismissed from the study.

Table 5

0 Month Maintenance Phase Double-Blinded Placebo Controlled Food Challenge Protocol		
Dose Number	Approximate Dose Amount (PEANUT PROTEIN)	Cumulative Dose Amount (peanut protein)
1	75 mg	75 mg
2	150 mg	225 mg
3	500 mg	725 mg
4	1000 mg	1725 mg
5	2000 mg	3725 mg
6	3000 mg	6725 mg
7	4000 mg	10725 mg
8	4500 mg	15225 mg
9	5000 mg	20225 mg
10	6000 mg	26225 mg

6.7. End of Study Food Challenge Visits (24 and 25 months after maintenance dose is reached) (approximately 8 hours per visit):

- Amount of blood to be drawn: At both visits, we will draw up to 4-6 tablespoons of blood (based on the subject's weight) for peanut-specific IgE, IgG, and IgG4, cellular immune studies, and basophil histamine release assays
- Allergy Skin Prick Tests (PST): Endpoint dilution skin testing to peanut will be done at the month 24 and month 25 visit.
- Spirometry or Peak Flow: Spirometry will be attempted in all participants. If valid spirometry results are not successfully obtained, the attempt is documented and peak flow measures will be accepted for the entry criteria with results >90% of predicted. For participants that are able to complete spirometry, FEV1 must be greater than 90% predicted on the day of the challenge to participate in the food challenge.
- Targeted History and Physical Exam and Diet History: A brief medical and diet history will be obtained and a focused physical exam will be performed.
- DBPCFC: The subject will come to Texas Children's Hospital in Houston for a Double Blind Placebo Controlled Food Challenge (DBPCFC) to the study protein (peanut) to determine if he or she is still allergic to peanut or can tolerate peanut.

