No subject initiating therapy in this trial will be replaced. The stopping rules for individual subjects are as follows:

- Greater than or equal to four missed or 'no-show' appointments and four missed home doses,
- Greater than 4 instances of not having or carrying an unexpired epinephrine injector to appointments
- Anaphylactic reaction listed as a Grade 4 as defined by the World Allergy Organization grading scale for systemic reactions to immunotherapy related to peanut OIT dosing at any stage of the protocol.
- Any participant is diagnosed with eosinophilic esophagitis
- Any participant is diagnosed with moderate to severe asthma based on the NHLBI guidelines
- Any participant needs treatment with greater than medium daily doses of inhaled corticosteroids, as defined by the NHLBI guidelines
- Any participant has an accidental peanut ingestion with anaphylaxis during the time on oral desensitization

Participants may be prematurely terminated from the study if:

- The participant elects to withdraw consent from all future study activities, including follow-up
- The participant is “lost to follow-up” (i.e., no further follow-up is possible because attempts to reestablish contact with the participant have failed)
- The participant dies

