9. MEASUREMENT OF EFFECT

9.1. Response Review:

The Data Safety Monitoring Committee will review the responses to the primary and secondary objectives every 6 months during the trial.

9.2. Response Criteria:

9.2.1. The primary objective will be measured by recording the daily symptoms experienced by the subjects and the number of subjects with no clinical symptoms during 6 g peanut flour challenge at time 50 weeks compared to time 0 weeks. The change in tolerated dose will be assessed between baseline and one year. The proportion of patients who tolerate 6 g of peanut flour will be compared at baseline and at the one year point using McNemar's test for matched pair data. The proportion of subjects will be estimated with exact binomial confidence intervals.

9.2.2. For the first secondary objective, flow cytometric analysis of T, NKT cells, and basophils will be performed through the measurement of the percent of cells producing a

cytokine as well as measuring surface and intracellular markers expressed upon activation and the significance of changes from time 0 to 1 year will be assessed as described below by using a paired t-test of the log-transformed data. Baseline measures of cell activation will be summarized by means with standard deviation. Normality will be assessed by quantile-quantile plots, and non-normality will be addressed by data transformations. A general linear mixed model will be used to estimate the effect of the therapeutic procedure over time. The model will include a fixed effect for time (discrete), and the matrix of correlated error terms will assume a first-order autoregressive structure. Alternative correlation structures such as the unstructured and compound symmetry will be considered. Correlation structures will be assessed by Akaike's Information Criteria. The likelihood ratio test will be used to test for overall significance of the model. P-values will be adjusted using the Holm's step down Bonferonni correction for multiple comparisons. Activation responses that are significant at the 0.05 level after adjustment will be further assessed. Pairwise comparisons between discrete time points will be tested for significant differences, and p-values will be adjusted using the Bonferonni correction. Statistical significance of the adjusted p-values will be assessed at the 0.05 level.

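### In 9.2.1 the McNemar comparison with baseline is uninformative about efficacy, because baseline tolerance is zero by design; the planned exact interval is the useful result but lacks a settled time point, challenge step and denominator

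*Combined protocol and SAP*

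**What the plan says.** The primary objective in 2.1.1 has a safety part, a change in tolerated dose, and the percentage of children who tolerate 6 g of peanut flour at a food challenge. For that percentage, 9.2.1 states: "The proportion of patients who tolerate 6 g of peanut flour will be compared at baseline and at the one year point using"; the method it goes on to name is McNemar's test for matched pairs. It adds that the proportion will be estimated with an exact binomial confidence interval.

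Eligibility fixes the baseline. Section 1 states: "In order to meet inclusion criteria subjects will not be able to tolerate a 1 gram peanut protein challenge". Section 3.1 requires "Significant clinical symptoms occurring within 120 minutes after ingestion of the last tolerated dose of peanut protein during the DBPCFC". In 6.3, "The table below labeled Table 2 details dosing for the initial DBPCFC"; its ten doses end at 2,000.5 mg cumulative protein.

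On timing, 2.1.1 places the challenge "following the initial desensitization phase of peanut flour which includes a 50 week dose escalation phase and 104 week maintenance phase", whereas 9.2.1 speaks of 50 weeks and of one year. On the challenge itself, 6.6 says "Peanut equivalent will be used for the food challenge at 0 month maintenance food challenge", and Tables 5 and 6 list their steps in mg of protein only.

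Section 10.1 plans 10 evaluable subjects and 15 enrolled, citing 50% attrition. Section 6.11 does not replace anyone who starts therapy, and its individual stopping rules include Grade 4 anaphylaxis related to dosing and "Any participant is diagnosed with eosinophilic esophagitis". No section names the analysis set for the proportion or says how a missing challenge is counted.

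**The concern.** A p-value against baseline will be read as evidence that the treatment works. Here the baseline value was created by selection, and there is no control arm, so the comparison cannot separate a treatment effect from retest variation or natural resolution. The estimate that can carry a conclusion is the proportion with its interval. As written, two analysts could report different rates from the same children, depending on which challenge they take, which step they call success, and whom they count. In a trial of 15, those choices move the result materially.

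**Working it through.** **The plan's own figure.** The only sample size given is for the IFN-gamma paired t-test in 10.1. SD of the difference = √(2 × 0.6² × (1 − 0.5)) = 0.6, so the standardised effect is 0.6/0.6 = 1.0. With n = 10 and two-sided alpha 0.05, power is 80.3%, so the 10 evaluable subjects reproduce. No sample size or precision is stated for the tolerance proportion.

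**Baseline is zero.** Flour column of Table 2: 1 + 2 + 10 + 30 + 108 + 150 + 200 + 500 + 1,000 + 2,000 = 4,001 mg, below 6,000 mg. The criterion dose is never reached at entry, and each enrolled child has reacted to less.

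**What McNemar's test then measures.** Let b be the children tolerant later but not at baseline, and c the reverse; c = 0 by design.

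- Exact two-sided: p = 2 × 0.5^b, a sign test on discordant pairs.
- Chi-square, uncorrected: (b − 0)²/(b + 0) = b.
- Chi-square, continuity-corrected: (b − 1)²/b.

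| b | exact p | uncorrected p | corrected p |
|---|---|---|---|
| 3 | 0.250 | 0.083 | 0.248 |
| 4 | 0.125 | 0.046 | 0.134 |
| 5 | 0.0625 | 0.025 | 0.074 |
| 6 | 0.031 | 0.014 | 0.041 |

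The number challenged appears in none of these formulas. The exact test needs six successes whatever the sample size. The plan does not say which version applies, and the uncorrected one needs only four. Four of 15 is 27% (95% CI 8 to 55), which would be significant by one version and not by the others.

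**Challenge step.** Table 3 pairs 6,000 mg of flour with 3,000 mg of protein, the same 2:1 ratio as Table 2. Cumulative protein in Tables 5 and 6 runs 75, 225, 725, 1,725, 3,725, 6,725 mg and on to 26,225 mg. So 3,000 mg is first passed cumulatively at dose 5 (3,725 mg) but first given as a single dose at dose 6. The plan does not say which is meant. Both exceed the entry ceiling of 2,000.5 mg, so baseline is zero on either reading.

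**Time point.** Section 2.1.1 gives 50 + 104 = 154 weeks; 9.2.1 gives 50 weeks or one year. The schedule has challenges at Months 0, 24 and 25 of maintenance. The 9.2.1 wording fits the Month 0 challenge and the 2.1.1 wording fits Month 24.

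**Denominator.** Clopper-Pearson 95% intervals for six successes:

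| denominator | rate | 95% CI | exact McNemar p |
|---|---|---|---|
| 15 (all enrolled) | 40% | 16 to 68 | 0.031 |
| 10 (evaluable in 10.1) | 60% | 26 to 88 | 0.031 |
| 8 (assumes about 50% of 15 lost) | 75% | 35 to 97 | 0.031 |

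The ratio between the first two rows is 15/10 = 1.5. All rows below the first assume that the attrition in 10.1, stated for IFN-gamma, also applies to the challenge.

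**The case against.** The test can be calculated and can reach significance, and six successes among at most 15 children do carry some information. The plan also already contains the informative analysis, so the p-value could be called merely redundant. That much stands: the fault in the test is that it is uninformative about efficacy, and a plan for the exact interval exists.

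Several stronger readings are tempting and are not supported.

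- A reader might infer that p is a probability under the hypothesis that no child becomes tolerant. It is not: one success would refute that hypothesis outright. The p-value is a sign-test probability on discordant pairs.
- A reader might infer that the trial is unlikely to reach six successes. That depends wholly on an assumed rate. With 10 challenged, the chance is 0.38 at a true 50%, 0.85 at 70% and 0.998 at 90%. Section 1 cites over 90% tolerating 3,900 mg in an open-label study.
- A reader might take the 6 g criterion as the 6,000 mg protein step, dose 10, since 6.6 says "The highest dose will be equivalent to approximately 34 peanuts" and 6,000/175 = 34.3 at Table 4's protein content per peanut. But 2.1.1 and 9.2.1 both say flour, and the 2:1 ratio is explicit. The live question is single or cumulative dose.
- A reader might infer that a rate among challenged children must be heavily biased upward. Section 6.12 keeps those who discontinue in the study, although it lists blood draws and monitoring and no challenge. Under the Appendix II algorithm, children with more than two Grade 3 reactions enter maintenance at their highest tolerated dose, so some dosing failures remain on course for the challenge. The bias is possible but limited.
- The 8 of 15 row is the extreme case; the plan's own figures give 10 of 15.

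**Conclusion.** The point holds and should be fixed. The comparison with baseline depends only on the success count, because eligibility and the entry challenge set the other side to zero; that follows from the documents without further assumption. The planned exact interval is the right result but cannot be produced unambiguously: 2.1.1 and 9.2.1 differ by 104 weeks, the criterion could be dose 5 or dose 6, and no denominator is set. The denominator alone moves six successes from 40% to 60%, given the assumption that 10 of 15 are challenged. The size of any bias in a challenged-only rate cannot be derived from the documents. Safety and the change in tolerated dose are also part of the primary objective and are not affected by this point.

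**What to change.** Delete the McNemar comparison with baseline from 9.2.1 and put in its place:

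> The proportion of all subjects who start OIT who complete the challenge step corresponding to 6 g peanut flour [step in mg protein, single or cumulative, to be stated by the sponsor] without clinical symptoms at [the challenge named once 2.1.1 and 9.2.1 are reconciled] will be reported with an exact binomial 95% CI. A subject without that challenge counts as not tolerant. The proportion among challenged subjects is a sensitivity analysis, with the reason for each missing challenge listed.

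The sponsor must reconcile the time point and tie the flour criterion to a step; Tables 5 and 6 have the same steps, so the text serves either challenge. Keep the planned change in tolerated dose from baseline and the safety outcome as parts of the primary objective.

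The cost is a few sentences in 9.2.1 and 2.1.1, with no new visits or data. The downside is that the rate is conservative and partly reflects retention: with 10 of 15 challenged it cannot exceed 10/15 = 67%. The sensitivity analysis shows how much of the shortfall is missing challenges. The p-value against baseline is lost.

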6.12. Follow-up of Discontinued Participants

Participants who prematurely discontinue treatment with study drug will remain in the study until normal termination. Subjects may receive the option of receiving a peanut equivalent if indicated. All willing subjects will be followed for the duration of the study, and continue blood draws for mechanistic studies while on a peanut restricted diet, and be monitored for accidental ingestions and safety parameters.

Procedure	Screening (Visit 1)	Entry Oral Food Challenge (Visit 2)	Buildup Phase Visit #3-28 (Weeks 0-50)	0 month of maintenance phase (Visit 29)	0 Month DBPCFC (Visit 30)	6 months maintenance phase (Visit 31)	12 months maintenance phase (Visit 32)	18 months maintenance phase (Visit 33)	24 months maintenance phase (Visit 34)	25 months maintenance phase (Visit 35)	End of Study Visit (Visit 36)	Unscheduled visits
Medical/Allergy Hx	X											
Spirometry or Peak Flow	X	X	X	X	X	X	X	X	X	X	X	X
Physical Exam	X	X	X	X	X	X	X	X	X	X	X	X
Diet Hx	X	X	X	X	X	X	X	X	X			X
Targeted Hx		X	X	X	X	X	X	X	X	X	X	X
Review Home			X	X	X	X	X	X	X			X
FAQLQ/F AIM											X	
Endpoint titration	X		X ¹	X			X		X	X		
Texas Children's Hospital in Houston OIT Administration			X	X ⁷							X	X
OIT Maintenance				X	X	X	X	X				
Entry Oral Food Challenge (1 gram of peanut protein)		X										
Oral food challenge					X				X	X		

Procedure	Screening (Visit 1)	Entry Oral Food Challenge (Visit 2)	Buildup Phase Visit #3-28 (Weeks 0-50)	0 month of maintenance phase (Visit 29)	0 Month DBPC FC (Visit 30)	6 months maintenance phase (Visit 31)	12 months maintenance phase (Visit 32)	18 months maintenance phase (Visit 33)	24 months maintenance phase (Visit 34)	25 months maintenance phase (Visit 35)	End of Study Visit (Visit 36)	Unscheduled Visit
Blood draw for immune cell studies		X	X ³		X	X	X	X	X	X		
Buccal mucosal scraping for HLA						X ⁸	X ⁸	X ⁸	X ⁸	X ⁸		
Pregnancy test	X ⁴				X ⁵		X ⁵		X ⁵	X ⁵		
Amount of blood to be drawn	1-2 tsp	4 – 6 tbs ⁶	4 – 6 tbs ^{3,6}		4 – 6 tbs ⁶	4 – 6 tbs ⁶	4 – 6 tbs ⁶	4 – 6 tbs ⁶	4 – 6 tbs ⁶	4 – 6 tbs ⁶		
Time required per visit	~3 hour	~9 hours	~3 hours	~3 hours	~9 hours	~1 hours	~1 hours	~1 hours	~9 hours	~9 hours	~3 hours	~3 hours

¹ will be obtained after 24 week build-up

² will check only peanut -specific IgE at the screening visit.

³ will be obtained at week 6, 12, 18, 24, 30, 36, 42, 48 of build-up phase only.

⁴Beta HCG serum pregnancy test

⁵ Urine pregnancy test

⁶Maximum amount of blood drawn (4 mL/kg)

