10. STATISTICAL CONSIDERATIONS

10.1. *Sample size considerations:*

Sample size was estimated to detect a statistically significant difference in the proportion of T cells producing interferon-gamma (IFN gamma), at the 1 year time point compared with baseline using a paired t-test. A difference in proportions of 0.60 units (.2 at baseline and .8 at 1 year) would be clinically important. Assuming a common SD=0.6 at each time point, correlation between repeated measures is 0.50 and alpha = 0.05, a sample size of 10 subjects would be required to detect this difference with 80% power. Assuming 50% attrition, this study will plan to enroll a total of 15 subjects.

Notes:

- 13 subjects for 90% power with alpha=0.01
- 16 subjects for 80% power with alpha=0.01
- 19 subjects for 90% power with alpha=0.01

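### The immune-marker mixed model treats gaps of about 4, 6 and 26 weeks alike, and its likelihood ratio test has no small-sample reference, so the overall test runs at about 6–12% rather than 5%

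*Combined protocol and SAP*

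**What the plan says.** Section 9.2.2 fits a linear mixed model with time as a discrete fixed effect to each T cell, NKT cell and basophil response. The default is that "the matrix of correlated error terms will assume a first-order autoregressive structure". It adds: "Alternative correlation structures such as the unstructured and compound symmetry will be considered". The choice is made by AIC: "Correlation structures will be assessed by Akaike's Information Criteria".

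For inference, "The likelihood ratio test will be used to test for overall significance of the model". Those p-values are Holm-adjusted. Markers that remain significant go on to a second stage: "Pairwise comparisons between discrete time points will be tested for significant differences, and p-values will be adjusted using the Bonferonni correction".

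The section does not state the time metric for the autoregression, the choice of ML or REML, the reference distribution of the likelihood ratio test, or a degrees-of-freedom method. It does provide a separate paired t-test for the change from time 0 to one year.

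The schedule of procedures shows immune draws at entry, during build-up (footnote 3: "will be obtained at week 6, 12, 18, 24, 30, 36, 42, 48 of build-up phase only"), at the month 0 challenge, and at months 6, 12, 18, 24 and 25. That is 15 draws, although section 7 says about 14. Section 6.7 puts the last two 4 weeks apart. Section 10.1 plans 15 children with 50% attrition and assumes that "correlation between repeated measures is 0.50".

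**The concern.** First-order autoregression over ordered visits sets the correlation between neighbouring draws to one value. Here neighbours are about 6 weeks apart in build-up, about 26 weeks apart in maintenance and 4 weeks apart at the end. If correlation falls with time, the model overstates it across 26 weeks, so those standard errors are too small. It understates it across 4 weeks, so that standard error is too large.

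Separately, a likelihood ratio statistic with 14 degrees of freedom does not follow chi-square closely when there are only 8–15 independent children. This test is the gate that decides which markers are examined further. Errors there decide which mechanistic changes are reported, and errors in the contrasts decide when those changes are said to occur.

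**Working it through.** **The plan's own figure.** Section 10.1: the SD of a difference is 0.6 × √(2 × (1 − 0.50)) = 0.6, so the standardised effect is 0.60/0.6 = 1.0. A two-sided paired t-test at 0.05 with n = 10 has 80.3% power, which reproduces the 10 subjects. The plan gives no error rate for the mixed model beyond the nominal 0.05. With 50% attrition, 15 enrolled leaves about 8 completers.

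**Unstructured.** 15 draws need 15 × 16/2 = 120 covariance parameters. After estimating 15 means, n children give a sample covariance of rank at most n − 1, so at most 14 for a 15 × 15 matrix. It is singular.

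**Gaps.** Suppose, as an assumption, that correlation is 0.50 at 52 weeks and decays exponentially. With the marker's variance set to 1, the variance of a difference is 2(1 − ρ):

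| Gap | ρ = 0.5^(gap/52) | 2(1 − ρ) |
|---|---|---|
| 4 weeks | 0.948 | 0.104 |
| 6 weeks | 0.923 | 0.154 |
| 26 weeks | 0.707 | 0.586 |

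The 26-week variance is 0.586/0.104 = 5.6 times the 4-week variance. Autoregression by visit order makes them equal.

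**Likelihood ratio test with the correlation known exactly.** With N = 15n observations, the test rejects when N × ln(1 + 14F/(N − 15)) exceeds 23.685, the 95% point of chi-square(14). F has 14 and N − 15 degrees of freedom.

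| n | N | F cut-off | True size |
|---|---|---|---|
| 8 | 120 | 1.636 | 8.1% |
| 10 | 150 | 1.649 | 7.4% |
| 15 | 225 | 1.665 | 6.5% |

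This part needs no assumption about correlation shape.

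**Simulation under no change over time.** Complete data, with draws at about weeks −2, 6 to 48 by 6, 52, 78, 104, 130, 156 and 160. The main runs used 3,000 data sets per setting (Monte Carlo error about 0.4 to 0.7 points). AIC chose between autoregression by visit order and compound symmetry.

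- *AIC choice.* Under decay in weeks it kept autoregression in 93.5–100% of runs. Under compound symmetry it chose compound symmetry in over 99%.
- *Overall test.* About 6–12% under decay in weeks (upper end at n = 8), and about 6–8% under compound symmetry.
- *After Holm.* Section 6.10 lists 25 markers, so the first threshold is 0.05/25 = 0.2%. Rejection at that level was 1.2–1.8% (n = 8) and 0.5–1.2% (n = 15) under decay, and 0.23–0.27% under compound symmetry.
- *Month 0 versus 6, unadjusted.* 15–19% under strong decay, about 9–13% with a child effect or noise or under faster decay, and about 5% under compound symmetry.
- *Month 24 versus 25, unadjusted.* 0.1–1.4% under pure decay, and up to about 3.5% with a child effect or noise.
- *Any of the 15 × 14/2 = 105 pairs after Bonferroni.* About 4–10% under decay in weeks if the overall-test gate is ignored. With the gate it is about 7–8% (checked for 0.50 at 52 weeks). Under the other shapes tried it is about 2–4%.

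**With weeks modelled, when decay in weeks is true.** The chi-square likelihood ratio test still gives 6.2–8.2%. A REML F test gives 4.9–5.7%, single pairs 4.0–6.5%, and any Bonferroni-adjusted pair 2.2–3.5%. Both changes are therefore needed.

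**The case against.** Several points on the other side stand.

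- The text does not say that autoregression is by visit order, that the reference is chi-square, or that all 15 draws enter one model. These are conventional readings. With only the 10 first-year draws, the overall test gives 6.0–8.2% and single pairs 1.8–8.9%.
- The list of alternatives is worded as open, so a time-based structure is not forbidden. It is not named either, and a plan should not depend on its being added later.
- Section 10.1 gives one correlation for two time points and no decay. If 0.50 is constant, AIC selects compound symmetry, pairs hold near 5%, and only the modest excess in the overall test remains.
- The comparison that sized the trial uses a paired t-test, which this problem does not touch.

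Two stronger readings are not supported. A reader might infer that the plan's 5% tests run as high as 19%. That figure is for unadjusted 26-week pairs under strong decay, whereas the plan gates and Bonferroni-adjusts its pairs. Averaged over all 105 pairs, the unadjusted rate under decay is 4.9–5.6%.

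A reader might also infer that month 24 versus 25 can hardly reject. The 0.1% is size under no change, not power. With correlation decaying from 0.50 at 52 weeks, a 1-SD shift is still detected after Bonferroni in 100% (n = 15) and 99% (n = 8) of runs. A 0.5-SD shift is detected in 59% and 9%, so the loss is for small shifts. The protocol's stated 24-to-25-month objective is dose tolerated, which is analysed elsewhere.

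**Conclusion.** The point holds in a limited form. As conventionally read, the default error structure ignores unequal gaps, no named alternative uses elapsed time, and one of the two cannot be fitted. The excess of the chi-square likelihood ratio test at 8–15 children is the firmest part: 6.5–8.1% even with the correlation known, and about 6–12% once the structure is misspecified under decay in weeks.

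The pairwise distortions run in both directions and depend on correlation falling with time. They vanish under compound symmetry. All simulated figures assume complete, balanced data. Dropout, and the differing build-up lengths that section 6.4 allows, were not modelled. Because the objective is secondary and mechanistic, this should be corrected but does not threaten the trial's main conclusions.

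**What to change.** In section 9.2.2:

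1. Add to the AIC candidates, alongside compound symmetry, a structure based on actual weeks since the entry challenge (spatial power, that is, continuous-time autoregression). Include a child random intercept and a residual term where they can be estimated. Both matter. When compound symmetry was true, decay alone pushed most pairs below 3% and a few up to about 10%. Without a residual term, the month 24 versus 25 contrast reached 11% once measurement noise was added.
2. Drop unstructured for the 15-draw model.
3. State which draws enter the model, and fit the final model by REML.
4. Replace the chi-square likelihood ratio test for time with a Kenward-Roger F test, and use the same degrees-of-freedom method for the pairwise contrasts. Name a parametric bootstrap as the fallback if the fuller model does not converge.

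The full model (intercept, decay, residual and Kenward-Roger together) has not been tested here at 8 children, so the fallback should be specified in advance. The cost is plan wording and a few lines of code. Some p-values will become less favourable. No extra visits or samples are needed.
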